2.2. Secondary endpoints

1. Percentage of patients achieving the CPDR of CD after 6 and 24 months of risankizumab.
2. Percentage of patients achieving clinical remission of CD (defined as HBI < 5) after 3 months, 6 months, 12 months and 24 months of risankizumab.
3. Percentage of patients showing clinical response of CD (defined as a reduction of the HBI of at least 3 points from baseline) after 3 months, 6 months, 12 months and 24 months of risankizumab. This endpoint will be assessed only in patients with an HBI > 5 at baseline.
4. Percentage of patients achieving endoscopic remission of CD (defined as SES-CD \leq 4 and at least a 2-point reduction vs baseline and no subscore >1 in any individual variable) after 3 months, 6 months, 12 months and 24 months of risankizumab.
5. Percentage of patients showing endoscopic response of CD (defined as a greater than 50% decrease in SES-CD from baseline (or for isolated ileal disease and a baseline SES-CD of 4, at least a 2-point reduction from baseline) after 3 months, 6 months, 12 months and 24 months of risankizumab.
6. Percentage of patients achieving the steroid-free “deep remission” of CD, defined as the combination of clinical remission and endoscopic remission according to the above-mentioned criteria (PMID: 26303131) after 6 months, 12 months and 24 months of risankizumab.
7. Percentage of CD patients achieving transmural healing at CT-scan or MRI enterography or at intestinal ultrasound (defined as a BWT \leq 3 and normal parietal contrast enhancement or color Doppler signal (CDS) or absence of hyperemia) after 3 months, 6 months, 12 months and 24 months of risankizumab.
8. Percentage of patients showing response of CD at radiological exams, including CT-scan or MRI enterography and intestinal ultrasound (defined as a decrease in BWT by 25% from baseline or 2.0 mm, or greater than 1.0 mm with a decrease in parietal contrast enhancement or in CDS assessed by the modified Limberg score of one grade) after 3 months, 6 months, 12 months and 24 months of risankizumab.

9. Variation of C-reactive protein (CRP) after 3 months, 6 months, 12 months and 24 months of treatment with risankizumab in CD patients.
10. Identification of clinical, endoscopic or radiologic predictors of deep remission in CD at 12 months and 24 months.
11. Percentage of patients achieving control of extraintestinal manifestation at 3 months, 6 months, 12 months and 24 months.
12. Comparison between the efficacy of risankizumab, as assessed according to the primary endpoint of the study, when used as second, third or fourth line of biological treatment.
13. Assessment of the safety of risankizumab during the entire study period.

3. Study design and investigational plan

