2.1. Primary endpoint

Primary endpoint of the study is the proportion of CD patients achieving steroid-free clinical-practice-deep remission (CPDR) after 12 months from baseline of treatment with Risankizumab, defined as the combination of:

patient reported outcomes (PRO) (patients reported abdominal pain \leq 1 and average stool consistency \leq 5 on Bristol Stool Scale without use of oral/intravenous steroids (prednisone-equivalent or budesonide) in the last 3 months)

AND an objective parameter of inflammation:

Faecal calprotectin <150 mcg/g, OR SES-CD \leq 4 and at least a 2-point reduction vs baseline and no subscore >1 in any individual variable, OR transmural healing at MRI/CT scan enterography or intestinal ultrasound, defined as BWT \leq 3 mm with no signs of active disease.

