4.2. Inclusion criteria

The participants must fulfill the following criteria for participating in the study:

1. Age of at least 18 years.
2. Patients with a previous diagnosis of CD at least 3 months before baseline.
3. Patients who have failed at least one advanced (biological or small molecule) therapy for CD and who have experienced failure to at least one mechanism of action (failure is defined as primary failure, secondary failure, or intolerance).
4. Patients, with any grade of clinical or endoscopic disease activity who have started a therapy with risankizumab for CD based on clinical practice indication (primary loss of response, secondary loss of response, intolerance to the previous drug).
5. Written informed consent certifying the willingness of the subject to participate to the study.

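### Endoscopic remission and deep remission require a 2-point SES-CD fall, which eligible patients with a baseline SES-CD of 0 or 1 can never achieve

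*Protocol*

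**What the plan says.** **Endpoint definitions (Protocol 2.2; the secondary aims use the same definitions).**

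- Endpoint 4, endoscopic remission: SES-CD of 4 or less, with "at least a 2-point reduction vs baseline and no subscore >1 in any individual variable".
- Endpoint 5, endoscopic response: "defined as a greater than 50% decrease in SES-CD from baseline (or for isolated ileal disease and a baseline SES-CD of 4", in which case a fall of 2 points is enough).
- Endpoint 6, steroid-free deep remission: "defined as the combination of clinical remission and endoscopic remission according to the above-mentioned criteria". It therefore carries the 2-point rule.
- Endpoint 10: a search for predictors of deep remission at 12 and 24 months.

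**Entry (Protocol 4.2 and 4.3).** Inclusion criterion 4 takes "Patients, with any grade of clinical or endoscopic disease activity who have started a therapy with risankizumab for CD based on clinical practice indication". The listed reasons for starting are "primary loss of response, secondary loss of response, intolerance to the previous drug". No exclusion criterion sets a minimum SES-CD.

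**Restriction by baseline activity.** For clinical response (endpoint 3) the protocol adds: "This endpoint will be assessed only in patients with an HBI > 5 at baseline". The secondary aims attach the same HBI restriction to clinical remission instead. Endpoints 4, 5 and 6 have no SES-CD counterpart in either place.

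**Primary endpoint (Protocol 2.1).** The objective component is "Faecal calprotectin <150 mcg/g, OR SES-CD \leq 4 and at least a 2-point reduction vs baseline" with no subscore above 1, or transmural healing on imaging. The three are alternatives.

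**The concern.** The entry criteria and the endpoint definitions do not fit together. A patient who switched because of intolerance may start risankizumab with little or no endoscopic inflammation. If that patient has SES-CD 0 at baseline and 0 at 12 months, endpoint 4 records no endoscopic remission, which is the opposite of what its name says.

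Two results are at stake. The reported rates for endpoints 4 and 6 would fall as the share of patients with nothing to improve rises, so they would be hard to compare with cohorts that have a different mix at entry. And in a predictor analysis of deep remission, any variable associated with inactive disease at baseline, such as a switch for intolerance, would tend to appear as a predictor of failure because of the definition alone.

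This is more than a detail left for the SAP. The protocol itself fixes these definitions, and it restricts the denominator by baseline activity for an HBI endpoint without doing so for the SES-CD endpoints.

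**Working it through.** **Plan's own figure.** The protocol gives no figure on this point. Its only worked precision example (section 4.4: proportion 0.5, n = 50, two-sided 95% interval, width 0.28945) is reproduced by the exact Clopper-Pearson interval, 0.35527 to 0.64473, and is not affected. The same interval method is used below.

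**Step 1: which baselines can succeed.** Let b be the baseline and u the follow-up SES-CD, both at least 0. By total score, remission needs u ≤ 4 and b − u ≥ 2. Response needs (b − u)/b > 0.5; the separate rule for isolated ileal disease at b = 4 is left out here.

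| b | u giving remission (endpoints 4, 6) | u giving response (endpoint 5) |
|---|---|---|
| 0 | none | none |
| 1 | none | 0 |
| 2 | 0 | 0 |
| 3 | 0–1 | 0–1 |
| 4 | 0–2 | 0–1 |
| 5 | 0–3 | 0–2 |
| 6 | 0–4 | 0–2 |

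Remission is impossible from 0 and 1. Response is impossible only from 0: a fall from 1 to 0 is a 100% decrease and counts. From 2 to 5 remission is possible, but the 2-point rule is stricter than the cut-off of 4. A patient who stays at SES-CD 2 with no subscore above 1 is also scored as a failure.

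**Step 2: effect on the rate.** Let f be the share of the analysed patients with baseline SES-CD 0–1, and r the rate among the rest. If all are counted,

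observed rate = r(1 − f) + 0 × f = r(1 − f), and the highest attainable rate is 1 − f.

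The protocol gives neither f nor r. The 50% to 60% in section 4.4 refers to CPDR, not to endoscopic remission. Over an assumed range:

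| r | f = 5% | f = 10% | f = 20% | f = 30% |
|---|---|---|---|---|
| 30% | 28.5% | 27% | 24% | 21% |
| 40% | 38% | 36% | 32% | 28% |
| 50% | 47.5% | 45% | 40% | 35% |
| Ceiling | 95% | 90% | 80% | 70% |

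**Step 3: against sampling error.** Take the planned 200 patients, all with a baseline SES-CD (an upper limit), r = 40% and f = 20%. Then 200 × 0.8 = 160 patients can succeed and 160 × 0.4 = 64 do. The rate is 64/200 = 32% (exact 95% CI 25.6% to 38.9%) over everyone, and 64/160 = 40% (32.3% to 48.0%) among those who can succeed.

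**Step 4: predictors.** In a model for deep remission as endpoint 6 defines it, the success probability at baseline SES-CD 0 or 1 is exactly zero, whatever the treatment does. Section 4.4 describes its predictor models for CPDR, whereas endpoint 10 names deep remission. The bias applies fully to the endpoint 6 outcome and only through one of three routes to CPDR.

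**The case against.** Several points on the other side have weight.

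- **The share may be small.** Every patient has failed at least one advanced therapy, and most of those with SES-CD 0–1 would plausibly come from the intolerance group. Nothing in the protocol supports f of 20% or 30% in particular. The wording on any grade of activity could also be read as requiring some activity, though no threshold is stated and a baseline of 1 would still be barred. This stands as a limit on size.
- **The denominator is not stated.** Section 5.1 collects endoscopic or radiologic monitoring, so not every patient need have an SES-CD, and an SAP could define the evaluable set. This stands in part: the dilution occurs only if these patients are counted. But as written nothing removes them, although the protocol makes such a restriction for HBI.
- **Requiring improvement is defensible.** Crediting remission only after a fall is a conservative choice in a single-group descriptive study. That may justify the rule for patients who can improve. It does not justify scoring as failures those for whom improvement is arithmetically impossible.

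A reader might also infer three stronger things that the protocol does not support:

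- **That the primary endpoint fails in the same way.** It does not. A patient with a normal bowel can still meet CPDR through calprotectin or transmural healing; the closed SES-CD route matters only if both of those are unmet or unmeasured.
- **That efficacy comparisons by line of therapy are distorted through endpoints 4 to 6.** Endpoint 12 and the Kaplan-Meier comparison in section 4.4 both use CPDR. No comparison of endpoints 4 to 6 by line is planned.
- **That the rates would no longer reflect drug effect.** The expression r(1 − f) depends on both, and r still drives it.

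**Conclusion.** The point holds for endpoints 4 and 6: an eligible patient with baseline SES-CD 0 or 1 cannot meet either. For endpoint 5 it holds only at baseline 0. The arithmetic is certain; the size is not. If these patients are counted, the relative loss in the observed rate for endpoints 4 and 6 equals f, so each 10 percentage points of f removes a tenth of r. For an assumed r of 50%, the rate runs from 47.5% at f = 5% to 35% at f = 30%. Both r and f are assumptions.

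The direction is towards understating endoscopic and deep remission. The predictor search in endpoint 10 is biased if its outcome is deep remission as defined in endpoint 6. The effect on the primary endpoint is partial and cannot be sized from the protocol. This is a defect in secondary endpoints that should be corrected before analysis; it does not undermine the primary result.

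**What to change.** Add one sentence to each endpoint in section 2.2, and to the matching secondary aims, parallel to the existing HBI restriction:

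- Endpoints 4 and 6 are assessed in patients with a baseline SES-CD of at least 2.
- Endpoint 5 is assessed in patients with a baseline SES-CD of at least 1.

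Use the same restriction in any model of predictors of deep remission under endpoint 10.

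Report separately, as maintained endoscopic remission, the patients who have SES-CD of 4 or less with no subscore above 1 at baseline and still do at follow-up. This group should include those with a baseline of 2 to 4 who do not fall by 2 points. The new cut-off alone would leave them visible only as failures.

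Give the number of patients at baseline SES-CD 0, 1 and 2–4, so that readers can see f. The data are retrospective and baseline SES-CD is already part of these endpoints, so no new data item is needed. The cost is a somewhat smaller denominator and a wider interval for these secondary endpoints: 160 instead of 200 patients in the example with f = 20%. Fixing the rule before analysis also prevents the denominator from being chosen after the rates are known.

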4. To evaluate the percentage of patients achieving endoscopic remission of CD (defined as SES-CD ≤ 4 and at least a 2-point reduction vs baseline and no subscore > 1 in any individual variable) after 3 months, 6 months, 12 months and 24 months of risankizumab.
5. To evaluate the percentage of patients showing endoscopic response of CD (defined as a greater than 50% decrease in SES-CD from baseline (or for isolated ileal disease and a baseline SES-CD of 4, at least a 2-point reduction from baseline) after 3 months, 6 months, 12 months and 24 months of risankizumab.

6. To evaluate the percentage of patients achieving the steroid-free “deep remission” of CD, defined as the combination of clinical remission and endoscopic remission according to the above mentioned criteria (PMID: 26303131) after 6 months, 12 months and 24 months of risankizumab.
7. To evaluate the percentage of CD patients achieving transmural healing at CT-scan or MRI enterography or at intestinal ultrasound (defined as a BWT \leq 3 and normal parietal contrast enhancement or color Doppler signal (CDS) or absence of hyperemia) after 3 months, 6 months, 12 months and 24 months of risankizumab.
8. To evaluate the percentage of patients showing response of CD at radiological exams, including CT-scan or MRI enterography and intestinal ultrasound (defined as a decrease in BWT by 25% from baseline or 2.0 mm, or greater than 1.0 mm with a decrease in parietal contrast enhancement or in CDS assessed by the modified Limberg score of one grade) after 3 months, 6 months, 12 months and 24 months of risankizumab.
9. To assess the variation of C-reactive protein (CRP) after 3 months, 6 months, 12 months and 24 months of treatment with risankizumab in CD patients.
10. To identify clinical, endoscopic or radiologic predictors of deep remission in CD at 12 months and 24 months.
11. To evaluate the percentage of patients achieving control of extraintestinal manifestation at 3 months, 6 months, 12 months and 24 months.
12. To compare the efficacy of risankizumab, as assessed according to the primary endpoint of the study, when used as second, third or fourth line of biological treatment.
13. To assess the safety of risankizumab during the entire study period.

2. Study endpoints

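### Radiological response (aim 8, endpoint 8) has no baseline wall-thickness requirement, so walls already at or below the plan's 3 mm healing limit enter the denominator and can count as responders

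*Protocol*

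**What the plan says.** Secondary aim 8 and endpoint 8 (section 2.2) use the same rule for response on ultrasound, CT or MRI: "defined as a decrease in BWT by 25% from baseline or 2.0 mm, or greater than 1.0 mm with a decrease in parietal contrast enhancement"; a one-grade fall in the modified Limberg Doppler score can take the place of the enhancement change. The limbs are alternatives, so a 25% fall in bowel wall thickness (BWT) is enough by itself. No baseline BWT is required.

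Entry does not supply one. Section 4.2, criterion 4, admits "Patients, with any grade of clinical or endoscopic disease activity who have started a therapy with risankizumab for CD", and no criterion mentions wall thickness. Intolerance of the previous drug is an accepted reason for starting, so patients with quiet bowel can be included.

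The plan does set a thickness limit for a healed wall. Endpoint 7 uses "defined as a BWT \leq 3 and normal parietal contrast enhancement or color Doppler signal (CDS) or absence of hyperemia", and the primary endpoint (section 2.1) uses the same 3 mm limit "mm with no signs of active disease".

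Other endpoints in section 2.2 carry a guard. For clinical response, endpoint 3 says: "This endpoint will be assessed only in patients with an HBI > 5 at baseline". Endoscopic remission (endpoint 4) requires "at least a 2-point reduction vs baseline and no subscore >1 in any individual variable". Endpoint 8 has no counterpart.

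**The concern.** A response rate is interpretable when everyone in the denominator had something that could improve. Here a patient whose wall already satisfies the thickness part of the healing definition is counted, with two consequences. Such a patient usually cannot improve much and is scored a non-responder, which pulls the rate down. When the two readings happen to differ by a few tenths of a millimetre in the right direction, the same patient is scored a responder, which pushes the rate up. Neither outcome says anything about the drug. The study has no control arm, so nothing offsets either effect, and the size of the distortion depends on how many such patients the centres enrol.

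**Working it through.** **The plan's own figure.** The only worked design figure is the interval width of 0.28945 for n = 50 and a proportion of 0.5 (section 4.4). It reproduces as an exact Clopper-Pearson interval (0.35527 to 0.64473), but has no bearing on this point.

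**Step 1: the smallest fall that qualifies without a change in enhancement or Doppler.** This is the smaller of 0.25 × baseline BWT and 2.0 mm.

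| Baseline BWT | Qualifying fall |
|---|---|
| 2.0 mm | 0.50 mm |
| 2.5 mm | 0.625 mm |
| 3.0 mm | 0.75 mm |
| 4.0 mm | 1.00 mm |
| 6.0 mm | 1.50 mm |
| 8.0 mm | 2.00 mm |

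At any baseline of 3 mm or less, a fall of 0.75 mm or less is enough. Example: 3.0 to 2.2 mm with unchanged Doppler is a fall of 0.8 mm, or 0.8/3.0 = 27%. It is a response, although the wall is within the 3 mm limit at both visits.

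**Step 2: how often noise alone produces a response.** Assume a true wall b that does not change, unchanged Doppler, and two independent readings X1 and X2, each with SD s. The rule takes 25% of the measured baseline, so the condition is X2 ≤ 0.75 × X1. The difference X2 − 0.75 × X1 has mean 0.25b and SD s × √(1 + 0.75²) = 1.25s. Hence

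P(false response) = Φ(−0.25b / 1.25s) = Φ(−0.2b/s).

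| True wall | s = 0.3 mm | s = 0.5 mm | s = 0.7 mm |
|---|---|---|---|
| 3 mm | Φ(−2.00) = 2.3% | Φ(−1.20) = 11.5% | Φ(−0.857) = 19.6% |
| 6 mm | Φ(−4.00) = 0.0% | Φ(−2.40) = 0.8% | Φ(−1.714) = 4.3% |

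A simulation that includes the 2.0 mm limb gives the same values to within 0.1 percentage points. The values of s are assumptions.

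**Step 3: the direction of the effect on the overall rate.** Take an assumed cohort: true BWT lognormal with median 4.5 mm and log-SD 0.35, s = 0.5 mm, 25% and 2.0 mm limbs only. In simulation, about 14.1% of patients have a measured baseline of 3 mm or less.

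- No drug effect: 5.2% respond overall and about 7.5% of those at 3 mm or less. Leaving the latter out gives (5.2 − 0.141 × 7.5) / 0.859 = 4.8%, so the rate falls.
- Assumed effect (half of patients with a true wall above 3 mm lose 35%): 38.0% respond overall and 13.9% of those at 3 mm or less. Leaving them out gives (38.0 − 0.141 × 13.9) / 0.859 = 42.0%, so the rate rises.

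The sign therefore depends on the drug effect, which is what the study is meant to estimate.

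**The case against.** **A relative-or-absolute composite is a legitimate choice, and aim and endpoint agree word for word.** This stands. The rule does not contradict itself; the gap is in the population to which it is applied.

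**The evaluable population could be set in a statistical analysis plan that is not shown.** Possible, but the protocol states such a restriction itself for endpoint 3, so silence at endpoint 8 reads as no restriction.

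**All magnitudes rest on assumed inputs.** This stands. The number affected among the 200 expected patients cannot be computed. That such patients are eligible and can respond follows from the text alone.

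**The 3 mm limit is only part of the healing definition.** Also true: a thin wall with hyperaemia is not healed. But at 3 mm or less the limb that uses Doppler or enhancement adds nothing, because a fall above 1.0 mm already exceeds 25%.

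**The Doppler condition might be meant to cover every limb.** The punctuation ties it to the 1.0 mm limb. On the wider reading, noise responses would be rarer, but the missing baseline requirement would remain.

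Three stronger readings are tempting and are not supported:

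- A reader might infer that the rule inflates the response rate. Step 3 shows that it can equally dilute it.
- A reader might infer that earlier treatment lines will look better. The planned comparison by line (endpoint 12) uses the primary endpoint, and the survival and Cox analyses in section 4.4 use CPDR; neither uses this rule. Nothing in the protocol says that earlier lines have thinner walls.
- A reader might infer that the 25% limb needs a 1.0 mm floor. That would redefine the composite for little gain: with no effect and s = 0.5 mm, restriction plus floor gives 4.2%, against 4.8% for restriction alone. It would also make a wall going from 3.8 to 2.8 mm with normalised Doppler healed under endpoint 7 but a non-responder under endpoint 8.

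**Conclusion.** The point holds as a gap in the population for endpoint 8. Patients with baseline BWT of 3 mm or less are eligible, are counted, and can respond on 0.75 mm or less. The chance of a response from noise alone is far higher for them than for thick walls: 11.5% at 3 mm against 0.8% at 6 mm, under an assumed reading SD of 0.5 mm. The net effect on the reported rate is of unknown sign and size, because the protocol gives neither the reading error nor the baseline BWT distribution. This is a secondary, descriptive endpoint; the primary endpoint does not use the rule and is unaffected.

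**What to change.** In secondary aim 8 and endpoint 8, state that radiological response is assessed only in patients with baseline BWT above 3 mm, in the way that endpoint 3 restricts clinical response by baseline HBI. Report how many patients with baseline imaging had BWT of 3 mm or less. Leave the three limbs of the rule as they are.

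The cost is one sentence in two places. No new data are needed, since the endpoint already requires a baseline measurement. The denominator becomes smaller, and the rate may move up or down. Responses on falls below 1.0 mm remain possible for baselines between 3 and 4 mm, and ordinary measurement noise is not removed. Making the change before the data are analysed avoids choosing the denominator after seeing the results.

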3.1. Overall study design

This is a multicenter, retrospective observational study with drug, including patients fulfilling inclusion and exclusion criteria, whom data required for the protocol are available.

We will include consecutive patients affected by CD, who have initiated Risankizumab and failed (already exposed) at least one mechanism of action (for anti TNF-alpha several molecules are allowed), until January 2024.

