4.3. Exclusion criteria

1. Age < 18 years.
2. Patients with diagnosis of indeterminate IBD.
3. Patients naive to advanced (biological or small molecule) therapy for IBD.
4. Refusal to sign written informed consent certifying the willingness of the subject to participate to the study.

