4.4. Sample size evaluation and statistical analysis

Based on the real-life study design and on the primary endpoint, which foresees a descriptive evaluation of remission rates according to each therapy line considered, we present diverse scenarios of potential sample size (from 50 till 300 by 25), and related confidence intervals in order to detect a CPDR at 12 months of 50-55 and 60% according to the evidence available from the current literature on the drugs under investigation. All scenarios are assessed according to a single group study design with a two-sided 95% confidence interval for a single proportion. A table with all potential scenarios will be provided as attachment.

As an example, such single-group design to obtain a two-sided 95% confidence interval for a single proportion, assuming a sample proportion of 0.5, with a sample size of 50, would produce a confidence

interval width of 0.28945, i.e., 0.5 ± 0.145 . The confidence interval widths were computed using PASS 2022, version 22.0.4 [29].

Based on the data available to the participating centers (for the retrospective phase) and the recruitment capabilities of the centers during the enrollment period, we expect to enroll 200 subjects with Crohn disease in this retrospective study.

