The evaluation of the difference in terms of CPDR at 12 months and 24 months, respectively, according to the different biological sequential therapies at II and III lines will be evaluated by Kaplan-Meier survival analysis. In particular, the log-rank test will be applied and appropriate cumulative incidence curves will be drawn. The analysis will be performed using the R packages “*ggplot2*” and “*survminer*” [31,32].

Potential predictors of CPDR will be assessed by Cox regression models. In detail, the potential predictors of the outcome will be evaluated by means of ordinary proportional hazards Cox regression models, and the Hazard Ratios (HR) and the 95% confidence intervals (CIs) will be reported. The proportionality of the hazard functions will be evaluated by visual inspection of the hazards and Schoenfeld residual plots. In case of doubtful proportionality, Cox weighted regression models will be

fitted. The analysis will be performed with "*survival*" and "*coxphw*" R packages [33-37]. Whether possible due to the different sample sizes of each therapeutic line and sequential strategy, to evaluate the combined effects between drug and line of administration, multivariable interaction models will be fitted, one per each predictor, and the interaction hazard ratios (IHR) reported. In summary, the coefficients of the main effects (in exponential terms) will be interpreted as HRs of the outcome by considering a unit increase of the predictor in the reference category (first line) (HR_{predictor}) as for quantitative predictors, whilst as increase in the hazard of the outcome occurring, as compared with the (arbitrarily) chosen reference group for qualitative data. The interaction parameters (IHR) will be interpreted as difference (in HR terms) of variations of the predictors among the different lines (first line as reference category).

5. Study procedures

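### The second-, third- and fourth-line groups of aim and endpoint 12 do not cover everyone the protocol enrols, and line has no single counting rule

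*Protocol*

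**What the plan says.** Secondary aim 12 (section on study aims) and secondary endpoint 12 (section 2.2) compare the primary endpoint across risankizumab "when used as second, third or fourth line of biological treatment". No section defines line or says how to count it.

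Prior treatment is described in other units elsewhere in the protocol:

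- Section 3.1 refers to patients who "failed (already exposed) at least one mechanism of action (for anti TNF-alpha several molecules are allowed".
- Inclusion criterion 3 (section 4.2) admits "Patients who have failed at least one advanced (biological or small molecule) therapy for CD", together with failure of at least one mechanism. It sets a minimum and no maximum.
- Exclusion criterion 3 (section 4.3) removes only "Patients naive to advanced (biological or small molecule) therapy for IBD". A patient who has had a small molecule and no biologic therefore stays in.

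Section 4.4 uses line in three ways. The sample size rationale foresees a "descriptive evaluation of remission rates according to each therapy line considered". The Kaplan-Meier comparison of CPDR is made "according to the different biological sequential therapies at II and III lines". The Cox interaction models compare predictors "among the different lines (first line as reference category".

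**The concern.** A grouping variable should place every enrolled patient in exactly one group. Here the groups are named in biologics, while the population is defined by advanced therapies and mechanisms. Two consequences follow.

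First, some eligible patients have no group in endpoint 12, although they count in the overall CPDR rate. Second, because no counting rule is given, the same drug history can be placed in different lines by different people, or a rule can be settled after outcomes are known, since the data are retrospective.

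Line carries much of the study's comparative content. CPDR is compared by line, adverse events are compared by line, predictors are interacted with line, and the sample size section speaks of remission rates by line. The three sets of lines in the protocol (second to fourth in aim and endpoint 12; second and third for Kaplan-Meier; a first-line reference for Cox) cannot all be followed by one analysis.

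**Working it through.** **The plan's own figure.** Section 4.4 gives a 95% interval width of 0.28945 for n = 50 and a proportion of 0.5. The exact (Clopper-Pearson) interval for 25/50 is 0.3553 to 0.6447, width 0.28945, so the figure reproduces. The simple normal approximation gives 0.2772 and is not what was used. The definition of line does not affect this figure.

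**Line by unit.** Take line = prior count + 1 and count the prior drugs in each unit that the protocol uses. The histories are illustrative, and all are eligible if the drugs failed.

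| Prior drugs | Biologics | Advanced therapies | Mechanisms |
|---|---|---|---|
| One anti-TNF | 2 | 2 | 2 |
| One small molecule only | 1 | 2 | 2 |
| Two anti-TNFs | 3 | 3 | 2 |
| One anti-TNF, one small molecule | 2 | 3 | 3 |
| Two anti-TNFs, one anti-IL-12/23 | 4 | 4 | 3 |
| Two anti-TNFs, one anti-integrin, one anti-IL-12/23 | 5 | 5 | 4 |
| The previous row plus one small molecule | 5 | 6 | 5 |

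Six of the seven change line with the unit. On endpoint 12's own unit (first column), rows two, six and seven fall outside lines 2 to 4. These histories were chosen to show the mechanism and say nothing about how common each is.

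**The first-line reference in section 4.4.** Every eligible patient has at least one prior advanced therapy and one failed mechanism, so by those counts line is at least 2 and the first-line category is empty. By biologics it holds only the small-molecule-only patients.

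**Patients outside the comparison.** Planned N is 200 (section 4.4). The share with no group is not given; assume 5% to 20%:

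- 200 × 0.05 = 10
- 200 × 0.10 = 20
- 200 × 0.20 = 40

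**Dilution from mixed counting.** Assume 80 second-line patients with CPDR 60% and 80 third-line patients with CPDR 40%, with drug count taken as the reference. Let a fraction f of the third-line patients (two anti-TNFs) be recorded as second line, with CPDR 40% among those moved. The recorded second-line rate is (48 + 80f × 0.40)/(80 + 80f), and the third-line rate stays at 40%.

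| f | Recorded second-line CPDR | Difference, points |
|---|---|---|
| 0 | 48/80 = 60.0% | 20.0 |
| 0.10 | 51.2/88 = 58.2% | 18.2 |
| 0.30 | 57.6/104 = 55.4% | 15.4 |
| 0.50 | 64/120 = 53.3% | 13.3 |

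For scale, the standard error of the 20-point difference with 80 per group is √(0.24/80 + 0.24/80) = 0.077, about 7.7 points.

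**The case against.** The best defence is that eligibility sets entry thresholds and does not number lines. Where the protocol attaches a unit to line, it is biological: in aim 12, in endpoint 12 and in the Kaplan-Meier sentence. Section 3.1 allows several anti-TNF molecules but does not say that they make up one line. Read literally, endpoint 12 gives one unit, and two prior anti-TNFs make risankizumab third line. Data go into one shared case report form, so line could be derived centrally. A cohort may also be broader than the groups of one secondary comparison, and derivation rules often sit in an analysis plan.

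Most of this stands. It limits the second consequence to what can happen: a reader might infer that sites will assign lines differently, but no section says that sites assign line at all. It does not remove the first. On the literal reading, small-molecule-only patients and those with four or more biologics still have no group, and the protocol does not say that they are left out on purpose. Nor can an analysis plan follow three different sets of lines.

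Two stronger readings are tempting and should not be made.

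- A reader might infer from the already-exposed parenthesis that sections 3.1 and 4.2 give different eligibility, for example for someone who stopped a biologic while well. Section 3.1 also requires the inclusion and exclusion criteria to be met, so the failure definition in section 4.2 governs. The parenthesis is loose wording.
- A reader might infer that line is the only comparison factor. Endpoint 10 and the Cox models also examine clinical, endoscopic and radiologic predictors.

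The dilution figures rest on an assumed scenario that treats drug count as the true line. The shrinkage of 1.8 to 6.7 points is smaller than the standard error of the difference.

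**Conclusion.** The point holds as a mismatch between the line categories and the enrolled population. Endpoint 12 as written leaves at least two kinds of eligible patient without a group, other histories move between lines with the unit, and section 4.4 names sets of lines that do not agree with aim and endpoint 12. This follows from the text and needs no assumption.

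Its size cannot be taken from the protocol. An assumed 5% to 20% share means 10 to 40 of 200 patients outside the comparison. The assumed 80/80 scenario gives a difference of about 18 to 13 points in place of 20.

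The overall 12-month CPDR proportion and the interval-width calculation are not affected. The correction should be made, but it concerns the by-line analyses and not the headline rate.

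**What to change.** Define line once, in the same words in aim 12, endpoint 12 and section 4.4, so that every eligible patient has a category. One workable rule is the number of prior advanced therapies for Crohn's disease plus one, each biologic or small molecule counting as one, grouped as second, third, and fourth or later. Counting biologics only, with added categories for the remaining patients, would also close the gap. The choice is the sponsor's, but counting small molecules does change the comparison that endpoint 12 now states, and the text should say so.

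Then:

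- Derive line centrally from the recorded list of prior drugs.
- Use the same set of lines in the Kaplan-Meier and Cox analyses, with second line as the reference in place of first.
- Repeat the comparison under the other counts (biologics only, failed mechanisms) as sensitivity analyses.
- Align the already-exposed wording in section 3.1 with the failure definition in section 4.2.

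The cost is protocol wording, one derived variable and some extra chart abstraction: eligibility needs only one qualifying failure, whereas line needs the full list of prior drugs. The open top group will be more mixed than a pure fourth-line group. Sample size and clinical management do not change.
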